6.5.2.1. Off-Treatment Visit Windows Relative to Last Dose for Safety

Patients who permanently discontinue study drug prior to Week 100 are asked to resume the planned assessments according to the study schedule in the protocol. Off-treatment values for clinical laboratory evaluations (Section 9.5), vital signs (Section 9.7), and electrocardiograms (Section 9.9) are those that occur after the last dose date for patients permanently discontinuing study drug prior to Week 100, and are summarized relative to their last dose of study drug. Off-treatment safety assessments (clinical labs, vital signs, and ECGs) are grouped for analyses according to the strategy in Table 5. Assessments that occur on or before the date of last dose through 20 days after last dose are considered on-treatment period.

Table 5: ANALYSIS VISITS FOR OFF-TREATMENT SAFETY FOLLOWING EARLY TREATMENT DISCONTINUATION

Off-Treatment Safety Analysis Visit	Label	Target Study Day (days after last dose)	Analysis Window
0	Last dose (on-treatment) ^a	0	0 (days after last dose ≤20)
4	Off Treatment 4-weeks ^b	28	21 ≤ days after last dose ≤ 35
8	Off Treatment 8-weeks ^b	56	36 ≤ days after last dose ≤ 71
12	Off Treatment 12-weeks ^b	84	72 ≤ days after last dose ≤ 99
24	Off Treatment 24-weeks ^b	168	100 ≤ days after last dose ≤ 252
48	Off Treatment 48-weeks ^b	336	253 ≤ days after last dose ≤ 350
72	Off Treatment 72-weeks ^b	504	351 ≤ days after last dose ≤ 518
96	Off Treatment 96-weeks ^b	672	519 ≤ days after last dose ≤ 686

^a Last dose for patients permanently discontinuing study drug prior to Week 100. Assessments that occur on the date of last dose or less than 21 days after last dose are considered on treatment and summarized using Table 4 windows.

^b The off-treatment values indicate the value closest to the date of last dose and at least 21 days after last dose.

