### **8.5.1. Study Drug Discontinuation Criteria**

Study drug discontinuation refers to a patient's stopping administration of study drug permanently. Reasons for study drug discontinuation may include the following:

- Adverse event;
- Death;
- Lost to follow-up;
- Physician decision;
- Pregnancy;

- Protocol specified criterion met (Section 7.4, Section 9.1.1, Section 9.1.9, Section 9.3.1, Section 9.6.1, Section 9.8.3);
- Withdrawal by patient;

To maximize patient retention and minimize missing data, patients who discontinue study drug early are encouraged to remain active in the study and complete all future study visits and assessments, except PKs and ABPM, if applicable.

For patients who discontinue treatment prior to Week 100, see Section 8.3.3 for the required off-treatment assessments. After the off-treatment assessments, the patient will continue with follow-up assessments through Week 112. The collection of laboratory data and vital status through Week 112 (B) is important for trial integrity, and data may be obtained through in-person clinic visits or through home health visits.

See Section 9.10.16 for Adverse Event Collection following study drug discontinuation.

For patients who are unwilling to complete all future visits, the Week 108 visit is of paramount significance. Collecting Week 108 data for all randomized patients is essential for trial integrity.

For patients who discontinue study drug and are no longer willing to return for all scheduled study visits, a number of follow-up options are available and must be discussed with the patient thoroughly, including:

- Participation in follow-up procedures specified in the protocol by an in-home visit, where feasible;
- Reduced in-person visit schedule;
- Telephone contact only;
- Contact of alternative person(s) who has been designated in source records as being available to discuss the patient's medical condition;
- Non-direct follow-up of patient information including obtaining additional information from the patient's medical records (e.g., ESKD or death).

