6.5.2. Visit Windows

Analysis visits and their windows are defined using derived study day (Section 6.5.1) instead of relying on visit labels in the clinical database because clinical visits may occur outside protocol-specified windows. Study day and days after last dose are calculated using the actual date of each scheduled and unscheduled assessment and compared to the target for each analysis visit as specified in Table 4 and Table 5. They are included in analyses of safety and efficacy as follows:

- Efficacy analyses for endpoints assessed through Week 100 use the analysis windows in Table 4, irrespective of whether or not a patient is receiving treatment of study drug.
- Efficacy analyses for endpoints assessed during the follow-up period after Week 100 use the analysis window in Table 4 irrespective of how long a patient has been off-treatment.
- Protocol version 6 eliminated the off-treatment period from Week 48 to Week 52. Patients completing the Week 52 visit prior to consenting to protocol version 6 will be considered “off-treatment” at Week 52. All other patients are expected to be on-treatment at Week 52. Week 52 analysis values in Table 4 will not be used in the efficacy analyses unless otherwise specified. Week 52 values are only summarized descriptively because of the mix of on-treatment and off-treatment values.
- Safety analyses use the analysis windows defined in Table 4 so long as the patient is receiving treatment of study drug. Once a patient permanently discontinues study treatment, safety data are summarized according to time since last dose as defined in Table 5.

Unless otherwise specified if a parameter is assessed or measured more than once within a visit window, the one that is closest to the protocol-scheduled time point (i.e., target) is used for the purposes of data analysis and summary.

If 2 assessments are equidistant from a target, the earlier assessment is used. If 2 assessments are on the same day, the average of 2 assessments will be used for non-laboratory parameters. For laboratory parameters, if both an original and retest result are available in the laboratory dataset, the original result will be used and the second (i.e., “retested”) result will be ignored.

One exception is that 2 scheduled chemistry values (including eGFR) are collected within the Week 52 (prior to protocol version 6), Week 104, Week 108, and Week 112 analysis windows.

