Protocol specified 2 off-treatment chemistry values collected within the Week 52 (prior to protocol version 6), Week 104, Week 108 and Week 112 analysis window at A and B visits. At Week 52, Week 104, Week 108, and Week 112 visits, the 2 off-treatment measurements that are in the analysis window and closest to the target day specified in Table 4 are averaged for the purpose of data summary and analysis. All values included in the Week 103, 104, 108, and 112 analysis windows must also be assessed after last dose.

Records from visits not closest to the target study day, and therefore not used in analyses, are presented in by-patient data listings.

Table 4. ANALYSIS VISIT WINDOWS

Analysis Visit	Label	Target		Analysis Window
		Study Day ^a	Days After Last Dose	
1	Week 1	7	-	$2 \leq \text{study day} \leq 10$
2	Week 2	14	-	$11 \leq \text{study day} \leq 21$
4	Week 4	28	-	$22 \leq \text{study day} \leq 35$
6	Week 6	42	-	$36 \leq \text{study day} \leq 49$
8	Week 8	56	-	$50 \leq \text{study day} \leq 70$
12	Week 12	84	-	$71 \leq \text{study day} \leq 126$
24	Week 24	168	-	$127 \leq \text{study day} \leq 210$
36	Week 36	252	-	$211 \leq \text{study day} \leq 294$
48	Week 48	336	-	$295 \leq \text{study day} \leq 350$
52	Week 52	364	-	$351 \leq \text{study day} \leq 406$
64	Week 64	448	-	$407 \leq \text{study day} \leq 490$
76	Week 76	532	-	$491 \leq \text{study day} \leq 574$
88	Week 88	616	-	$575 \leq \text{study day} \leq 658$
100	Week 100 ^b	700	-	$659 \leq \text{study day} \leq 720$
103	Week 103 ^c	721	21	$721 \leq \text{study day} \leq 727^{\text{d}}$ or $21 \leq \text{after last dose} \leq 27^{\text{e}}$
104	Week 104 ^c	728	28	$728 \leq \text{study day} \leq 755^{\text{d}}$ or $28 \leq \text{after last dose} < 55^{\text{e}}$
108	Week 108 ^c	756	56	$756 \leq \text{study day} \leq 783^{\text{d}}$ or $56 \leq \text{after last dose} \leq 83^{\text{e}}$
112	Week 112 ^c	784	84	$784 \leq \text{study day} \leq 806^{\text{d}}$ or $84 \leq \text{after last dose} < 106^{\text{e}}$

^a Study Day is relative to the date of first dose (Section 6.5.1).

^b Week 100 is the end of the dosing interval and should coincide with the last dose.

^c Including off-treatment values only.

^d Analysis windows are based on study day for patients who discontinued treatment early. Analysis windows are based on days after last dose for patients who complete treatment. Last dose for analysis is the Week 100 dose.

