9. SAFETY AND TOLERABILITY

Safety and tolerability are evaluated by AEs, SAEs, clinical laboratory test results, body weight, vital signs, 12-lead ECG findings. All analyses of the safety data are performed using the safety analysis set. Descriptive statistics are presented by treatment group assignment in the safety analysis set. Statistical testing is not performed for safety analyses unless otherwise specified. On-treatment values are summarized according to the analysis study windows in Section 6.5.2; Off-treatment values are summarized according to the analysis study windows in Section 6.5.2.1. Safety data summaries are grouped by treatment.

Continuous safety parameters (including selected clinical chemistries and vital signs) may be summarized using the methodology described in Section 8.4.1, and Section 8.5.1. Only the visit windows outlined in Table 4 and Table 5 are included in these analyses.

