9.5.2. Categorical Summaries of Laboratory Results

Select laboratory parameters will be summarized using shift tables. Shift tables are summarized by treatment, laboratory category (hematology, chemistry, urinalysis, and microscopy), and laboratory test and present shifts from baseline status (Normal, Low, High) to worst on study treatment status (Normal, Low, High). The worst abnormality values are defined as the maximum values while on study treatment (i.e., up to <21 days after last dose), with the exception of magnesium and hemoglobin. The worst abnormal values for magnesium and hemoglobin are defined as the minimum values while on study treatment (i.e., up to <21 days after last dose).

Additionally, laboratory parameters of specific interest (ALT, AST, ACR, BNP) are summarized using shift tables that summarize shifts from (1) baseline status to end of treatment status, (2) worst on-treatment status to worst off-treatment status, (3) worst on-treatment status to end of study, and (4) baseline status to worst on-treatment status 5) baseline to worst off-treatment, and (6) worst on-treatment status to best (lowest) off-treatment status. The number and percentage of patients are summarized. For ACR, summaries will present shifts from/to the categories listed in Section 6.5.5.1. For ALT and AST, summaries will present shifts from/to the following categories:

- \leq ULN
- $>$ ULN to $<3 \times$ ULN
- $\geq 3 \times$ ULN to $<5 \times$ ULN
- $\geq 5 \times$ ULN to $<10 \times$ ULN
- $\geq 10 \times$ ULN to $<20 \times$ ULN
- $\geq 20 \times$ ULN

For BNP, summaries will present shifts from/to the following categories:

- <100 pg/mL
- ≥ 100 pg/ml to <200 pg/ml
- ≥ 200 pg/ml to <400 pg/ml
- ≥ 400 pg/ml

In addition, a summary table is provided for the number and percentage of patients meeting a following pre-specified threshold level at any time during the study:

- ACR >3500 mg/g
- Magnesium <1.3 mEq/L (0.65 mmol/L)
- BNP >200 pg/mL
- NT-proBNP >1000 pg/mL

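### SAP 6.5.2.1 limits off-treatment safety values to patients who stop before Week 100; this contradicts SAP 6.5.2, Table 4 and 9.5.1 and leaves completers without a clear status in the 9.5.2 off-treatment shift tables

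*SAP*

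**What the plan says.** SAP 6.5.2.1 states that off-treatment laboratory values, vital signs and ECGs "are those that occur after the last dose date for patients permanently discontinuing study drug prior to Week 100". Table 5, which supplies the windows, has the same scope: its title is "ANALYSIS VISITS FOR OFF-TREATMENT SAFETY FOLLOWING EARLY TREATMENT DISCONTINUATION", and its footnote a describes last dose in the same early-stopping terms. Section 9 then says "Off-treatment values are summarized according to the analysis study windows in Section 6.5.2.1" and gives no separate rule for patients who finish treatment.

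The fourth bullet of SAP 6.5.2 is worded differently. It says "Safety analyses use the analysis windows defined in Table 4 so long as the patient is receiving treatment of study drug", and then "Once a patient permanently discontinues study treatment, safety data are summarized according to time since last dose as defined in Table 5". Neither sentence mentions Week 100.

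Table 4 has rows for Weeks 103, 104, 108 and 112, marked "Including off-treatment values only". Its footnotes d and e count those windows from the Week 100 dose for patients who complete treatment. SAP 9.5.1 averages the A and B chemistry values at Weeks 104, 108 and 112.

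SAP 9.5.2 lists six shift tables for ALT, AST, ACR and BNP. Three need an off-treatment status: "worst on-treatment status to worst off-treatment status", baseline to worst off-treatment, and worst on-treatment to best off-treatment.

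**The concern.** A patient who takes the Week 100 dose is no longer receiving drug, so the first sentence of the 6.5.2 bullet takes that patient out of Table 4 for safety. Nor did the patient stop before Week 100, so 6.5.2.1 does not call the later values off-treatment. Two programmers could each defend a different table: one with completers in the off-treatment shifts, one without.

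The second version would be the poorer analysis. Whether changes in transaminases, BNP and albuminuria reverse off drug is a natural use of the follow-up that protocol 8.3.3 plans for 12 weeks after 100 weeks of dosing. Showing it only in early stoppers selects patients by something that happens after randomisation and may depend on treatment, and it leaves out the group for whom the period was planned. It would also mix tolerability stops with administrative stops from the sponsor's termination.

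**Working it through.** The plan states no figure on this point, so the check is a reading of the rules side by side and a mapping of visits to windows.

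**1. Which rule covers a completer after Week 100?**
- 6.5.2, Table 4 for safety: only while on drug, so no.
- 6.5.2, Table 5: after permanent discontinuation, so yes if the planned stop counts. Protocol 8.5.1 describes discontinuation as "stopping administration of study drug permanently", which does not exclude the planned stop, and protocol 8.3.3 speaks of discontinuation at the planned Week 100 point as well as earlier. SAP 7.1, however, separates completing treatment from discontinuing it.
- 6.5.2.1, Table 5 title and footnote a: early stoppers only, so no.
- Table 4 rows for Weeks 103 to 112 and SAP 9.5.1: completers appear, but 9.5.1 concerns chemistry and does not define off-treatment status for the shifts.

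**2. Do completers' visits have windows?** Visit days are from the schedule of assessments, in days after last dose.

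| Visit | Days | Table 4 row | Table 5 window, if it applied |
|---|---|---|---|
| 103 | 21–25 | 103 (21–27) | 4-week (21–35) |
| 104 A | 28–35 | 104 (28 to <55) | 4-week |
| 104 B | 29–36 | 104 | 4-week; day 36 goes to 8-week (36–71) |
| 108 A, B | 56–64 | 108 (56–83) | 8-week |
| 112 A, B | 84–92 | 112 (84 to <106) | 12-week (72–99) |

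Every scheduled visit falls in a window of both tables. What is missing is a rule saying which table governs.

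**3. What data are affected?** Each completer is scheduled for chemistry at all 7 off-treatment visits, and for BNP, ACR, vital signs and ECG at 2 (104 B and 108 B). In 9.5.2 the exposure is 3 shift types × 4 parameters = 12 shift summaries.

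**4. Who is a completer?** SAP Section 2 dates the drug-termination notice to 10 May 2023. By SAP 6.5.1, study day = date − first dose + 1. Day 700 on 10 May 2023 therefore means a first dose 699 days earlier, on 10 June 2021; using the 5-day early allowance (day 695), 694 days earlier, on 15 June 2021. If dosing ended at the notice, anyone first dosed later stopped before Week 100 and already meets the 6.5.2.1 definition. The documents do not give each patient's stop date or the number on either side.

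**The case against.** The best defence is that the SAP already accommodates completers twice. Table 4 has off-treatment rows built for them, and the safety chapter uses those visits: 9.5.1 averages chemistry there, and Section 9 names both tables for its optional modelled summaries. Alternatively, the 6.5.2 bullet read with protocol 8.3.3 puts them in Table 5. SAP 9.5.2 also ends the on-treatment period at less than 21 days after last dose with no Week 100 limit, and its natural complement includes completers. Separate displays for the two groups are a legitimate choice in descriptive safety summaries.

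Most of this stands. A reader might infer that completers' safety data fall under no rule at all, or go largely unused; the documents do not support that, because windows exist and at least the chemistry is summarised. The defence does not settle the matter, though. The two accommodating readings point to different tables, and the only passage that defines off-treatment safety values, the one Section 9 relies on, excludes completers.

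The defence is also right that simply moving completers into Table 5 would create new trouble. Footnote b takes the value nearest the last dose, so in the 4-week window Week 103 would displace the Week 104 A/B average, and a Week 104 B visit on day 36 would land in the 8-week window.

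**Conclusion.** The point holds as an internal contradiction with a real consequence if 6.5.2.1 is followed to the letter: the twelve off-treatment shift summaries would omit everyone who completed Week 100. It does not hold as a clear exclusion of completers from all off-treatment safety reporting.

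Its size in patients cannot be stated. A reader might assume that 15–30% of 425 per arm stop early (425 × 0.15 = 64; 425 × 0.30 = 128) and infer that 70–85% of patients are lost from these tables. That rate is not in the documents, and it supposes a trial that ran to plan, whereas the termination moved an unknown number of patients inside the definition. A reader might also infer that the early-stopper group is mainly selected by treatment effects; sponsor termination stopped both arms for a reason unrelated to assignment, so that too is unsupported. What can be said is per completer: seven chemistry visits, and two visits each for BNP, ACR, vital signs and ECG, with an unclear status.

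**What to change.** - In 6.5.2.1, delete the restriction to stopping before Week 100 and define off-treatment safety values for all patients as those at least 21 days after the permanent last dose. This matches the on-treatment cut-off already in 6.5.2.1 and 9.5.2.
- In 9.5.2, state that completers are included in the worst and best off-treatment shifts, pooled by arm.
- In 6.5.2 and Section 9, state that completers' by-visit safety summaries use the Week 103 to 112 rows of Table 4. Table 5 can then remain the by-visit scheme for early stoppers.
- If a pooled 4-, 8- and 12-week display is added, map completers' Week 104, 108 and 112 analysis values (A/B averages for chemistry) to those time points and exempt them from Table 5 footnote b. Early stoppers also have a visit 21–25 days after last dose (protocol 8.3.3), so say how their 4-week value is chosen. Keep the completer and early-stopper split as supportive.

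The cost is SAP wording and a small programming change before database lock. No new data are needed.

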6.5.3. Laboratory Evaluations Imputations

Any laboratory assessments less than the lower limit of detection (i.e., < LLD) are imputed as LLD/2 (e.g., <25 is 25/2=12.5). Laboratory assessments above the upper limit of detection (ULD) are imputed as the ULD. If the lab result is qualitative but presented as >X and X is 10 times greater than the ULN, then the value X is used in the analysis.

6.5.4. eGFR

The eGFR is calculated using the formula below according to patient's age at the date of consent. The formula will not change throughout the study. The Chronic Kidney Disease Epidemiology Collaboration (CKD-EPI) equation is used for adult patients (age at consent at least 18 years):

- $eGFR \text{ (mL/min/1.73 m}^2\text{)} = 141 \times \min(S_{cr}/\kappa, 1)^\alpha \times \max(S_{cr}/\kappa, 1)^{-1.209} \times 0.993^{\text{Age}} \times 1.018 \text{ [if female]} \times 1.159 \text{ [if black]}$

For Adolescents (≥ 12 and < 18 years age old at consent) - the eGFR value will be calculated by using Bedside Schwartz equation:

- $eGFR \text{ (mL/min/1.73 m}^2\text{)} = (0.41 \times \text{Height in cm}) / S_{cr}$

where S_{cr} is serum creatinine (mg/dL), κ is 0.7 for females or 0.9 for males, and α is -0.329 for females or -0.411 for males. Min indicates the minimum of S_{cr}/κ and 1, and max indicates the maximum of S_{cr}/κ and 1. Age and height indicates at time of serum creatinine collection as collected in the associated case report form (CRF).

6.5.4.1. Prognosis of CKD by eGFR and Albuminuria Category

Prognosis of chronic kidney disease (CKD) is determined by the intersection of the following eGFR and albuminuria categories ([KDIGO, 2013](#)):

Figure 2: PROGNOSIS OF CKD BY eGFR AND ALBUMINURIA CATEGORIES

				Persistent albuminuria categories Description and range		
				A1	A2	A3
				Normal to mildly increased	Moderately increased	Severely increased
				<30 mg/g <3 mg/mmol	30–300 mg/g 3–30 mg/mmol	>300 mg/g >30 mg/mmol
GFR categories (ml/min per 1.73 m ²) Description and range	G1	Normal or high	≥90			
	G2	Mildly decreased	60–89			
	G3a	Mildly to moderately decreased	45–59			
	G3b	Moderately to severely decreased	30–44			
	G4	Severely decreased	15–29			
	G5	Kidney failure	<15			

Green: low risk (if no other markers of kidney disease, no CKD); yellow: moderately increased risk; orange: high risk; red, very high risk.

The Prognosis of Kidney Disease: Improving Global Outcomes (KDIGO) CKD progression risk scores is summarized by cell and color (Green, Yellow, Orange and Red).

Table 6. CKD STAGE

CKD ^a Stage	eGFR ^b (mL/min/1.73 m ²)
1	≥90
2	60 to <90
3a	45 to <60
3b	30 to <45
4	15 to <30
5	<15

^a Chronic kidney disease

^b Estimated glomerular filtration rate

Table 7. ALBUMINURIA CATEGORY

ACR ^a Category	ACR (mg/g)
1 (normo-albuminuria)	<30
2 (micro-albuminuria)	30 to ≤300
3 (macro-albuminuria)	>300

^a Urine albumin to creatinine ratio

6.5.5. Urine Albumin to Creatinine Ratio (ACR)

ACR is provided in the central laboratory database as the ratio of urine albumin to urine creatinine from the first morning void (FMV) urine collection. The ACR value is not calculated in the central laboratory database when the FMV urine albumin result is < LLD. Urine albumin results < LLD and the corresponding ACR missing values are imputed as follows:

- If urine albumin result ≤LLD, then
 - Imputed urine albumin result (mg/dL)=LLD/2
 - Imputed ACR (mg/g)=(imputed urine albumin result in mg/dL)/[(urine creatinine in mg/dL)/1000]

The ACR results are log-transformed for analysis to produce data that are more normally distributed. Any imputed ACR result where ACR=0 is considered to be 0.1 mg/g for purposes of calculating the geometric mean.

6.5.5.1. Baseline Urine Albumin to Creatinine Ratio (ACR) Categorical Status

Baseline ACR status will be grouped by the following categories using baseline ACR (see Section 6.4.5):

- ACR ≤300 mg/g
- ACR >300 mg/g

Baseline ACR accounts for screening and Day 1 values and may not match ACR used for stratification based on screening values only.

6.5.5.2. eGFR Category used in Stratification (eGFR_STRAT)

The eGFR category used for stratification (eGFR_STRAT) is determined by the randomization list with the following categories:

- 30 mL/min/1.73 m²<eGFR<60 mL/min/1.73 m²
- 60 mL/min/1.73 m²≤eGFR≤90 mL/min/1.73 m²

